## 8.1.2. Effectiveness

All enrolled subjects meeting all inclusion and exclusion criteria that receive the LimFlow Stent Graft System (e.g., implanted) will be included in the effectiveness analyses, as Per Protocol population (PP).

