## 5.1.1. Pre-operative Inclusion Criteria

- 1. Subject must be  $\geq$  21 and  $\leq$  95 years of age
- 2. Clinical diagnosis of symptomatic critical limb ischemia, defined as any of the following clinical assessments coupled with hemodynamic evidence of severely diminished arterial inflow of the index limb (e.g., absent pulse(s), TcPO2 < 30 mm Hg):
  - a. Rutherford Classification 5, ischemic ulceration
  - b. Rutherford Classification 6, severe ischemic ulcers or frank gangrene
- 3. Subject has been assessed by the principal investigator, and reviewed by the Independent Safety Committee (ISC), and it was determined that no conventional distal bypass surgical or endovascular therapy for limb salvage is feasible due to the absence of a suitable distal target artery.
- 4. Proximally, the Target In-flow Artery at the cross-over point must be treatable with a 3.5– 4.0 mm stent after pre-treatment (by visual estimate), and be <50% stenosed
- 5. Prior stent(s) to the Target In-flow Artery are allowed

- 6. Planned minor amputation of target extremity within 30 days after the index procedure is allowed
- 7. Subject is willing and able to sign the informed consent form
- 8. Subject has an adequate support network to ensure that subject is compliant with medication regimen and follow-up study visits

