## 5.1.2. Exclusion Criteria

- 1. Concomitant hepatic insufficiency, thrombophlebitis, deep venous thrombus, or coagulation disorder
- 2. Pre-existing immunodeficiency disorder or receiving immunosuppressant therapy
- 3. Prior peripheral arterial bypass procedure above or below the knee which could inhibit proximal inflow to the stent graft.
- 4. Previous major amputation of target limb
- 5. Life expectancy less than 12 months
- 6. Documented myocardial infarction or stroke within previous 90 days
- 7. Known or suspected active infection at the time of the index procedure that may preclude insertion of a prosthesis
- 8. Known or suspected allergies or contraindications to aspirin / dual antiplatelet therapy, heparin, stainless steel, nitinol or contrast agent that cannot be adequately pre-treated
- 9. Subject is currently taking warfarin, which in the opinion of the investigator interferes with the subject's ability to participate in the study (i.e., intermittent interruption of therapy for procedure may compromise subject's safety)
- 10. Lower extremity venous disease with significant edema in the target limb that may inhibit the procedure and/or jeopardize wound healing, in the investigator's opinion.
- 11. Significant acute or chronic kidney disease with a serum creatinine of > 2.5 mg/dl, and/or requiring dialysis.
- Severe heart failure, which in the opinion of the investigator may compromise subject's ability to safely undergo a percutaneous procedure (e.g., known ejection fraction of < 40%, NYHA Classification III-IV)
- 13. Any significant concurrent medical, psychological, or social condition, which may significantly interfere with the subject's optimal participation in the study, in the opinion of the investigator
- 14. The subject is currently participating in another investigational drug or device study that has not completed the primary endpoint or that clinically interferes with the endpoints of this study
- 15. Subject is unwilling or unable to comply with any of the protocol or follow-up requirements
- 16. Prior to enrollment, women of childbearing potential must have a negative urine pregnancy test

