## 6.4 Study Procedures

#### 6.4.1 Enrollment

Once any component of the LimFlow Stent Graft System is introduced into the body, the subject will be considered to be enrolled in the study and subject to all follow-up requirements. If the device is introduced but implantation is either not attempted or unsuccessful, subjects will be followed through 30 days for safety only, or through resolution or stabilization of any device- or procedure- related adverse events, whichever is longer. Those subjects will then be exited from the study and will not be replaced.

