# **8.0 Statistical Considerations**

## 8.1 Analysis Populations and Data Handling Conventions

## 8.1.1. Safety

All subjects who receive any portion of the LimFlow Stent Graft System will be included in safety analysis, as Intent to Treat population (ITT).

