## 8.2.3. Effectiveness

## 8.2.3.1. Secondary Effectiveness Analysis

The secondary effectiveness endpoints will be summarized for the effectiveness study sample per 8.1.2. Summary statistics for the Composite (rate and 95% confidence interval) will be reported. The proportion of LimFlow Stent Graft subjects who are converted to other treatment means due to technical failure will also be reported.

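### Effectiveness is analysed only in implanted subjects who met every eligibility criterion, with no all-implanted analysis and no rule that decides later exclusions without reference to outcome

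*Combined protocol and SAP*

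**What the plan says.** Section 8.1.2 defines the effectiveness set, labelled Per Protocol, as "All enrolled subjects meeting all inclusion and exclusion criteria that receive the LimFlow Stent Graft System", with receipt taken to mean implantation. Section 8.2.3.1 applies it: "The secondary effectiveness endpoints will be summarized for the effectiveness study sample per 8.1.2". No all-implanted, all-enrolled or sensitivity analysis of effectiveness is given. Safety differs: section 8.1.1 counts everyone who received any portion of the system, whether or not every criterion was met.

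Eligibility is placed before treatment. Section 5.1 requires all criteria to be satisfied before enrolment. Section 6.2 has the investigator conclude on eligibility and the Independent Safety Committee (ISC) review the candidate before enrolment. Table 1 schedules the inclusion/exclusion assessment at Visit 1 only. Enrolment itself is defined in section 6.4.1: "Once any component of the LimFlow Stent Graft System is introduced into the body, the subject will be considered to be enrolled".

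Some criteria rest on judgement. Exclusion 15 reads "Subject is unwilling or unable to comply with any of the protocol or follow-up requirements". Inclusion 8 asks for a support network adequate to secure compliance with medication and visits. Exclusion 10 concerns venous disease that might, in the investigator's opinion, harm wound healing, which is itself an endpoint.

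**The concern.** Every implanted subject has already been judged eligible. For these subjects the eligibility clause in 8.1.2 is therefore either redundant or removes someone whose deviation came to light after enrolment. That could plausibly happen: section 9.2 provides periodic monitoring for protocol adherence, and section 14.2 requires source evidence of eligibility. By then the outcome may be known, because the study is single-arm and open.

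The plan names no decision-maker, no time point and no blinding for this step. If removals fall more often on failures than on successes, the reported patency, wound-healing and limb-salvage rates rise, and the renal-deterioration rate may fall, with no change in device performance. The rates would also no longer describe everyone in whom the device was implanted. The study tests no hypothesis, so what is at stake is the reported rates and their confidence intervals, not type I error.

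**Working it through.** **Does the plan close the gap?** There is no planned figure to reproduce: section 8.3 gives no power calculation or performance goal. The first check is therefore on the text.

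1. Timing of the eligibility judgement: before the procedure (5.1, 6.2, Table 1).
2. Rule for a deviation found later: 8.1.2 excludes the subject from effectiveness, because the criteria were not all met.
3. Who decides, when, and blind or not: not stated in 8.1 or 8.2. The adjudication list in section 10.2 covers outcomes and does not mention Per Protocol membership.
4. Wider-set backup. Amputation-free survival at 30 days and 6 months uses the safety set (8.2.2.1, 8.2.2.2), so limb loss and death to 6 months are covered. Patency, wound healing, renal function, and limb salvage at 9 and 12 months have no such backup.

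**How far could a rate move?** Let *x* be successes, *N* implanted subjects and *k* failures removed.

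- Reported rate = x/(N − k)
- Gain = x/(N − k) − x/N = xk/[N(N − k)]

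Inputs: N = 35, the maximum in section 4.2, all assumed implanted. The documents give no expected rate for this trial, so *x* and *k* are assumptions. Row A assumes 20 patent at 6 months. Rows B and C borrow the 1-year surgical figures quoted in section 1.1, 71% foot preservation and 46% secondary patency, giving x = 25 and x = 16.

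| Row | k = 0 | k = 2 | k = 4 | Gain (points) |
|---|---|---|---|---|
| A, x = 20 | 20/35 = 57.1% | 20/33 = 60.6% | 20/31 = 64.5% | 3.5 to 7.4 |
| B, x = 25 | 25/35 = 71.4% | 25/33 = 75.8% | 25/31 = 80.6% | 4.3 to 9.2 |
| C, x = 16 | 16/35 = 45.7% | 16/33 = 48.5% | 16/31 = 51.6% | 2.8 to 5.9 |

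Gains for row A: 20 × 2/(35 × 33) = 40/1155 = 3.5 points; 20 × 4/(35 × 31) = 80/1085 = 7.4 points.

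For scale, the exact 95% interval for 20/35 is about 39% to 74%, so both shifted rates lie inside it. With only the 10 subjects that section 8.3 calls sufficient, the effect is larger: 7/10 = 70.0% becomes 7/8 = 87.5% if two failures are removed.

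**The case against.** The strongest reply is that eligibility is already fixed in time. Sections 5.1 and 6.2, the synopsis and Table 1 all place it before the procedure, and section 1.3.2 says ISC screening ensures that the criteria are met. No section provides for re-judging it. This largely stands: a reader might infer that the plan lets failures be reclassified as never eligible, and the documents do not say that. What remains is narrower. These sections say when the criteria apply, not how analysis-set membership is settled if a deviation emerges later. Section 10.2 also describes the ISC's screening task mainly as confirming that no conventional option is feasible. Its open-ended list of evidence does not name compliance or support network.

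Some tempting examples also fail:

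- **Early death.** "Life expectancy less than 12 months" is a prognosis at screening, and a death at month 4 does not show that it was breached. Nor is death clearly a patency or limb-salvage failure under section 7.3, so removing that subject need not raise either rate.
- **In-flow artery.** The criterion that the vessel be treatable "after pre-treatment (by visual estimate), and be <50% stenosed" is settled no later than the procedure, before any patency, limb or wound outcome.
- **Stopping medication.** Later non-adherence does not by itself show that the support network was inadequate at entry.

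The counts in the illustration are assumed, and nothing in the documents suggests that such removals will occur. Finally, a Per Protocol set decided from baseline records may nearly equal the all-implanted set. That is a reason to make the all-implanted set the main one, since it then costs little.

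Technical success is a separate matter: analysed in a set that requires implantation, it loses its failures by definition. The change proposed here does not address that.

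**Conclusion.** The point holds as an unprotected analysis set. The only effectiveness population can lose implanted subjects after enrolment, and the plan has neither a rule for deciding this without reference to outcome nor an analysis that keeps those subjects in. The possible bias is in patency, wound healing, and 9- and 12-month limb salvage.

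On assumed counts of 20 patent among 35 implanted, removing 2 to 4 failures adds 3.5 to 7.4 points. Across the three assumed rates the range is 2.8 to 9.2 points. These figures assume that all 35 are implanted and that every removed subject is a failure; if removals were unrelated to outcome, no systematic shift would be expected.

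The documents do not support a finding that outcomes will be used to redefine eligibility, or that limb loss is hidden: through 6 months it is counted in amputation-free survival. The change is worth making because it is cheap, but the primary endpoint is not affected.

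**What to change.** In sections 8.1.2 and 8.2.3.1, define the population for patency, limb salvage, wound healing and renal function as all enrolled subjects implanted with the stent graft, regardless of eligibility deviations found later. Keep Per Protocol as a supportive analysis only. State that its membership is decided from the eligibility and procedural records without reference to outcome, and list each excluded subject with the criterion breached.

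No new assessments are needed, because implanted subjects are already under the full follow-up requirements (section 6.4.1). The cost is a wording change, one extra set of tables and possibly slightly less favourable rates. If no deviations are found, the two sets coincide and the extra tables add nothing.

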#### 6.4.2. Intra-operative

At a minimum, all subjects must be started on dual anti-platelet therapy (DAPT) at least 1 week before the procedure or adequately pre-loaded with DAPT according to the institution's practice. For consented subjects that meet the pre-operative eligibility criteria, record the relevant data regarding their endovascular procedure. Record the following information:

- Target In-Flow Artery (cross-over point), including proximal reference vessel diameter (RVD) and assessment of calcification or any other abnormalities
- Target Out-Flow Vein (cross-over point) characteristics
- Intra-operative anticoagulants administered, and corresponding ACT levels
- Pre- and post-procedural angiographic images showing flow to the foot
- Procedure start and finish times
- Total contrast amount given
- Total fluoroscopy time for the procedure
- Documentation of any device- or procedure-related adverse events
- Technical Success

At the end of the endovascular procedure, with the procedural sheath in place and under fluoroscopic visualization, an injection of contrast will be made to assess the anatomy, placement and patency of the proximal, body and distal ends of the Stent Graft.

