# 7.3 Secondary Effectiveness Endpoints

There are multiple secondary effectiveness endpoints to be evaluated in the study:

- **Primary Patency at 30 days**: Defined as the absence of total occlusion of the stent graft without prior clinically driven major re-intervention of the stent graft at 30 days.
- **Primary Patency at 6 months**: Defined as the absence of total occlusion of the stent graft without prior clinically driven major re-intervention of the stent graft at 6 months.
- Secondary Patency at 6 months: Defined as the absence of total occlusion of the stent graft with or without prior clinically-driven major re-intervention of the stent graft at 6 months.

• **Deterioration in Renal Function at 6 months:** Defined as a 25% increase in serum creatinine after using iodine contrast agent without another clear cause for kidney injury.

• Limb Salvage at 3, 6, 9, and 12 months: Defined as percentage of subjects with freedom from above-ankle amputation of the index limb.

• Wound Healing at 3, 6, 9, and 12 months: Defined as percentage of subjects with completed index wound healing.

• Technical Success: Percentage of technical success, defined as completion of the endovascular procedure and immediate morphological success with successful placement of the arterial and venous catheters in the desired location in the limb, and ability to place the stent graft.

• **Procedural Success:** Percentage of subjects with a procedural success, defined as combination of technical success, and absence of all-cause mortality, above-ankle amputation or clinically-driven major re-intervention of the stent graft through 30 days.

 Occlusion is defined as absence of flow on color Doppler, and/or absence of flow on angiographic images (conventional or CT).

 Clinically-driven major re-intervention is defined as the creation of a new surgical bypass, the use of thrombectomy or thrombolysis (i.e., procedures done in the setting of lost primary-assisted patency), or major surgical revision such as a jump graft or an interposition graft performed for critical occlusion of the stent graft.

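### Technical Success and Procedural Success are analysed only in eligible, implanted subjects, so failed placements cannot lower either rate

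*Combined protocol and SAP*

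**What the plan says.** Four statements in the combined protocol and SAP settle the denominator.

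- **Endpoints (7.3).** Technical Success and Procedural Success are both listed as secondary effectiveness endpoints. Technical Success covers "completion of the endovascular procedure and immediate morphological success", correct catheter placement, "and ability to place the stent graft". Procedural Success is Technical Success plus freedom from death, above-ankle amputation and major re-intervention of the graft through 30 days.
- **Analysis rule (8.2.3.1).** "The secondary effectiveness endpoints will be summarized for the effectiveness study sample per 8.1.2". No endpoint is exempted.
- **Population (8.1.2).** The sample is enrolled subjects who meet all eligibility criteria and "that receive the LimFlow Stent Graft System (e.g., implanted) will be included in the effectiveness analyses, as Per Protocol population (PP").
- **Enrollment (6.4.1).** A subject is enrolled once any component of the system enters the body. The section foresees subjects who are enrolled but not implanted: "If the device is introduced but implantation is either not attempted or unsuccessful, subjects will be followed through 30 days for safety only", or longer if related adverse events have not settled. It then says: "Those subjects will then be exited from the study and will not be replaced".

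Section 8.1.1 places everyone who receives any portion of the system in the safety population, labelled ITT, but uses that population for safety only. Section 8.2.3.1 adds that the proportion of subjects "who are converted to other treatment means due to technical failure will also be reported". It does not give the denominator of that proportion.

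**The concern.** The two endpoints are meant to show how often the procedure can be carried out as intended. Under the stated rule, a subject in whom the graft could not be placed is removed from numerator and denominator alike. The placement component of Technical Success is then met by everyone left in the sample, and Procedural Success inherits the same selection.

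Feasibility is a stated objective (synopsis and section 3.0), and these two rates bear on it most directly. The study is single-arm with no hypothesis test, so the reported rates and their intervals are the result. If any placement fails, a reader would see rates that look better than the experience of the enrolled subjects.

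**Working it through.** The documents state no success rate, target or expected failed-placement rate, so there is no figure of the plan's own to reproduce. The first step is to trace who is counted; the second is to size the effect under stated assumptions.

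**Step 1: who is counted**

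| Enrolled subject (6.4.1) | Safety set (8.1.1) | Effectiveness set (8.1.2) | Effect on Technical Success as planned |
|---|---|---|---|
| Eligible, implanted, good morphology | in | in | success |
| Eligible, implanted, poor morphology | in | in | failure |
| Implantation not attempted or unsuccessful | in | out | none |

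The second row shows that the planned rate is not fixed at 100%. An implanted subject can still fail on morphology, which the Independent Safety Committee (ISC) judges from the procedural angiograms (10.2). It is failure to place the graft that cannot register.

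**Step 2: formula**

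Let N be the number enrolled, k the number not implanted and s the number of successes, all of them among the implanted. Assume all enrolled subjects are eligible.

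- Planned rate: s / (N − k)
- All-enrolled rate: s / N
- Gap: s·k / [N(N − k)], which is never negative and is zero only if k = 0 or s = 0

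**Step 3: numbers**

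N = 35 is the maximum in section 4.2. The values of k and the failures among the implanted are assumptions. Intervals are exact (Clopper-Pearson) 95%.

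Technical Success, no other failures (s = 35 − k):

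| k | Planned | All enrolled | Gap (points) |
|---|---|---|---|
| 0 | 35/35 = 100% (90.0–100) | 35/35 = 100% (90.0–100) | 0 |
| 2 | 33/33 = 100% (89.4–100) | 33/35 = 94.3% (80.8–99.3) | 5.7 |
| 4 | 31/31 = 100% (88.8–100) | 31/35 = 88.6% (73.3–96.8) | 11.4 |
| 6 | 29/29 = 100% (88.1–100) | 29/35 = 82.9% (66.4–93.4) | 17.1 |

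Technical Success, 2 morphological failures among the implanted (s = 33 − k):

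| k | Planned | All enrolled | Gap (points) |
|---|---|---|---|
| 0 | 33/35 = 94.3% (80.8–99.3) | 33/35 = 94.3% (80.8–99.3) | 0 |
| 2 | 31/33 = 93.9% (79.8–99.3) | 31/35 = 88.6% (73.3–96.8) | 5.4 |
| 4 | 29/31 = 93.5% (78.6–99.2) | 29/35 = 82.9% (66.4–93.4) | 10.7 |
| 6 | 27/29 = 93.1% (77.2–99.2) | 27/35 = 77.1% (59.9–89.6) | 16.0 |

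Procedural Success, 3 failures of any kind among the implanted (s = 32 − k):

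| k | Planned | All enrolled | Gap (points) |
|---|---|---|---|
| 0 | 32/35 = 91.4% (76.9–98.2) | 32/35 = 91.4% (76.9–98.2) | 0 |
| 2 | 30/33 = 90.9% (75.7–98.1) | 30/35 = 85.7% (69.7–95.2) | 5.2 |
| 4 | 28/31 = 90.3% (74.2–98.0) | 28/35 = 80.0% (63.1–91.6) | 10.3 |
| 6 | 26/29 = 89.7% (72.6–97.8) | 26/35 = 74.3% (56.7–87.5) | 15.4 |

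The planned rate barely moves as placement failures rise. The small drift in the last two tables comes only from holding the number of other failures fixed over a shrinking denominator. A single failed placement with no other failure gives 34/34 = 100% against 34/35 = 97.1%, a gap of 2.9 points.

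**Step 4: the eligibility restriction**

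Section 8.1.2 also drops subjects who are implanted but ineligible, and their successes would raise the all-enrolled rate. Let j be the number of such subjects, all successes, and m the number of failures among the eligible implanted; s now counts the eligible successes only. The planned rate s/(s + m) falls below the all-enrolled rate (s + j)/(s + m + j + k) only if s·k < j·m. With N = 35, k = 1 and m = 2, s = 32 − j, so the condition is 32 − j < 2j, or j of at least 11. Pre-enrollment ISC review makes that many ineligible subjects unlikely.

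**The case against.** The strongest reply is that placement failures are not hidden. Section 8.2.3.1 promises the proportion converted because of technical failure, and section 6.6 requires the date and reason of exit for subjects enrolled but not implanted. With at most 35 subjects, a reader who is given the enrolled count and the exit reasons could rebuild the all-enrolled rate. This stands as partial mitigation. However, the conversion proportion has no stated denominator, it may miss procedures abandoned without conversion, and it enters neither success rate.

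Second, section 8.1.2 offers implantation only as an example of receiving the system, and section 2.1 counts the catheters and valvulotome as part of the system. A looser reading is therefore possible. But section 8.1.1 uses any portion for the safety set, and 8.1.2 uses the whole system together with a Per Protocol label, so implantation is the natural reading. If the sponsor meant otherwise, the text still needs correcting.

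Third, both endpoints are secondary and descriptive, with no performance goal or decision rule attached, and the size shown above rests wholly on assumed counts. Both points are true. They limit the consequence without removing the mismatch.

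Finally, safety-only follow-up of non-implanted subjects and the ban on imputation (8.1.3) might seem to rule out counting them. They do not. Table 1 places Technical Success at the treatment visit, and a subject who fails it has failed Procedural Success by definition, so nothing has to be imputed.

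**Conclusion.** The concern holds. Read together, 7.3, 8.2.3.1, 8.1.2 and 6.4.1 remove enrolled subjects without a placed graft from the two endpoints that should count them as failures. Apart from the remote eligibility case in Step 4, the resulting bias is in the favourable direction.

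Its size depends on a failed-placement count that the documents do not give. With 35 enrolled, all eligible, and 2, 4 or 6 not implanted, Technical Success is overstated by about 5–6, 11 and 16–17 points, and Procedural Success (3 failures among the implanted) by about 5, 10 and 15 points. With no failed placements there is no effect. The primary endpoint, 30-day amputation-free survival in the 8.1.1 population, is untouched. This should be fixed; it does not undermine the study.

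**What to change.** Amend 8.1.2 and 8.2.3.1 as follows.

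1. Analyse Technical Success and Procedural Success in all enrolled subjects as defined in 6.4.1, and state that this is the same set as the 8.1.1 population.
2. Count subjects in whom implantation was not attempted or was unsuccessful as failures on both endpoints.
3. Report exact 95% confidence intervals, and keep the Per Protocol result as supportive.
4. Use all enrolled subjects as the denominator for the proportion converted because of technical failure.
5. Keep patency in implanted subjects. For Limb Salvage and Wound Healing, state that results apply to implanted subjects only: 6.4.1 plans no follow-up of the others beyond 30 days or the settling of related events, and 8.1.3 bars imputation.

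The cost is a wording change. No visit, measurement or follow-up rule changes. Technical Success is already scheduled at the treatment visit in Table 1, and it is among the items to be recorded under 6.4.2: "For consented subjects that meet the pre-operative eligibility criteria, record the relevant data regarding their endovascular procedure". The only downside for the sponsor is a less favourable reported rate if any placement fails.
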